Hypothesis: The hypothesis of the large scale trial is that High volume Foleys will decrease the risk of cesarean delivery compared to prostaglandins. **The hypothesis of the current pilot study is that a randomized controlled trial is possible, in that we can enroll 20% of eligible women.**

PROJECT NARRATIVE PROPOSAL

Background:

Approximately 1/3 of first-time mothers (nulliparous women) undergoing induction of labour deliver by cesarean¹. Cesarean delivery can have negative consequences to the initial^{4,5,6} and subsequent⁷ pregnancies. Women who have a cesarean in their first pregnancy are more likely to have a cesarean in their following pregnancies¹ and this group is the largest contributor to the overall cesarean delivery rate¹. Therefore, targeting interventions that prevent cesareans in nulliparous women undergoing induction of labour will have a substantial impact on the overall cesarean delivery rate.

Adequate ripening or preparing the cervix before induction has been found to decrease the risk of cesarean⁸⁻¹¹. This can be done by a variety of methods, such as prostaglandins (a chemical messenger) or a Foley filled to a moderate volume of fluid. These methods have been found to be equal regarding the risk of cesarean delivery¹². **However, a meta-analysis by our team discovered a trend towards a decreased risk of cesarean when cervical ripening is undertaken with Foleys filled to a high volume of fluid (80cc) compared to those filled to a low volume (30cc)³.**

Most Canadian Obstetricians use prostaglandins for cervical ripening². To assess if 80cc Foleys result in a lower risk of cesarean, they need to be compared to the Canadian standard of prostaglandins. Therefore a randomized controlled trial is required.

The Greater-Toronto-Area Obstetric (GTA-OB) Network is a group of hospitals committed to facilitating research and will be the setting for the planned large scale trial. The large scale trial will aim to demonstrate a difference in the rate of cesarean from 38% to 31%, which will require the enrolment of 1442 women. It has been estimated that there are 5,437 women who will meet entry criteria in the GTA-OB network each year, if 1/2 are approached, 20% will need to consent to complete the trial in 3 years. **Therefore, this pilot study will determine if this recruitment rate is potentially achievable and will inform design strategies to ensure its success.**

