[name]: Neonatologist at Sunnybrook Health Sciences Center, Neonatal Research Director for the Department of Newborn and Developmental Pediatrics at Sunnybrook. Associate Professor in the departments of Pediatrics and Obstetrics and Gynecology at University of Toronto. She has contributed to the design and will contribute to the analysis. (1hr/ week)

[name]: Tier II Canada Research Chair, Associate Professor in the Department of Obstetrics and Gynecology at McMaster University, Associate Member of the Department of Clinical Epidemiology and Biostatistics. She has contributed to the design and will contribute to the analysis. Interpretation of the data, and knowledge translation (1 hr/ week).

[name]: Maternal-Fetal Medicine specialist at Mount Sinai Hospital, Associate Professor in the Department of Obstetrics and Gynecology and Institute of Health Policy, Management and Evaluation at University of Toronto. She has contributed to the design and will contribute to the analysis, interpretation of the data, and knowledge translation (and organize recruitment through Mount Sinai. (1hr/ week)

[name]: Scientist and statistician at the Sunnybrook Research Institute, Assistant Professor in the department of health policy, management and evaluation at the University of Toronto. He will contribute to the analysis.

Approach and Work Plan

Study Design: The proposed study is a multicentre open label **randomized controlled trial pilot**. It will include nulliparous (women who have never given birth) women with term pregnancies requiring cervical ripening prior to induction of labour and takes place at Sunnybrook and NorthYork General Hospitals . The intervention involves randomizing women to cervical ripening with either a Foley filled to 80cc, or prostaglandins. We will register the trial at Clinicaltrials.gov

Primary research question: What is the probability that eligible women will agree to be randomized into the trial evaluating high volume Foleys to prostaglandins for cervical ripening.

Primary outcome: The percentage of eligible women who are approached to participate in the study that are enrolled and randomized to either the use of a high volume Foley or prostaglandin for cervical ripening.

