Other outcomes: A rolling assessment of **the study process** to evaluate issues that may affect enrolment rates. These will be evaluated under the categories of technical, environmental, staff personnel, patient, and data collection issues. Other important processes outcomes include protocol compliance, ease of intervention, physician and patient satisfaction.

Inclusion criteria

- Nulliparous women 37 weeks and 0 days to 41 weeks and 6 days gestational age (term) requiring cervical ripening
- Health care provider feels it is possible to administer either method of cervical ripening.
- Bishop score of 6 or less
- Live, singleton, cephalic fetus

Exclusion Criteria

- Non-viable fetus
- Contraindication to cervical ripening, labour induction or labour
- Prior attempt at induction of labour in this pregnancy
- Spontaneous rupture of fetal membranes
- Evidence of labour or regular uterine contractions
- Lack of consent
- No one available to perform randomisation

How will participants be identified and followed?

An educational session for nurses, midwives, residents and physicians will be done at each centre. A detailed study information package will be available to give to women who meet entry criteria. Patients may choose to sign a consent form for the study in the antenatal period, or on presentation for cervical ripening.

Patients presenting for cervical ripening and meeting entry criteria will be invited to participate in the study and informed consent will be obtained by the research assistant. The research assistant will access the online randomization service at the Sunnybrook clinical trials unit, and the patient will be randomized to either prostaglandin or Foley filled to 80cc. At this time, all care and decision-making will be provided as per the woman's care provider. All approached women, whether they consent to be part of the study or not, will be invited to complete a short questionnaire regarding knowledge of the study prior to the day of induction and feelings towards research.

RAs will record in Redcap the date and time of delivery for enrolled women, as well as mode of delivery (vaginal or cesarean section) and any serious adverse events (maternal death or ICU admission, neonatal death or unplanned ICU admission)

Data Collection

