Data collection for patient information will be collected electronically through RedCap. Semi-structured interviews from physicians, nurses, and residents will be conducted by the PI or delegate and recorded on paper or via email.

Patient knowledge and satisfaction surveys will be provided by the research assistant and completed by the patients when approached about participating in the study.

How will outcome measures be captured?

The primary outcome measure of percent of women recruited will be captured by the number of women who undergo the randomized intervention divided by the number of women who are eligible. These numbers will be kept by the research assistants enrolling participants in the trial. Demographic data for recruited women will be captured by the research assistants from patient charts.

For process outcomes, semi-structured interviews will be conducted with staff, chief residents and charge nurses and will be recorded in writing. Patients will be asked to fill a short patient satisfaction survey. These process outcomes will be captured every 3 months.

[figure not shown]
Analysis:

The primary outcome is a descriptive statistic of number of women enrolled/ number of eligible women. Process outcomes that are quantitative in nature will be described using descriptive statistics. Qualitative process outcomes will be evaluated via group discussion and consensus at each steering committee meeting.

Sample Size calculation

The primary outcome is the proportion of eligible women who consent and are randomized into the pilot trial. It is estimated that 10-15 women will be approached per week over a 15 month time frame. This is based on a total population of 4000 deliveries per year at Sunnybrook and 6000 at North York General Hospital. . One half are nulliparous, and 90% are term. 25 % of these women will undergo induction of labour, meaning approximately 24 women per week. Not all inductions will take place during day time hours or during weekdays at Sunnybrook, however almost all inductions at North York General are pre-scheduled to take place in the afternoon during the workday, resulting in an approximation of 10-15 women approached per week or 630-975 women approached over a 15 month time frame. Our target proportion is 20%. For an expected consent rate of 20%, the sample of 130-195 will provide the 95% confidence interval around this estimate to have bounds ranging from 16.9% to 23.3%, and from 17.5% to 22.7% respectively

Timeline

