The start-up time includes hiring of RAs, ethics, contracts and data sharing agreements, information sessions and distribution of study information materials.

Recruitment and data collection will take place in 3 month blocks. The recruitment rate and feedback from clinicians will be assessed at a steering committee meeting every 3 months, after which strategy changes will be implemented.

The final analysis will take place in the final 3 months of the study.

Project Outcome Evaluation Metrics

Anticipated outcomes:

The primary outcome will be the percent of eligible participants approached for the trial that are enrolled in the trial and undergo randomization. **A recruitment rate of at least 20% will be considered a success.**

Outcome	Method of capture
Recruitment rate	Number of women enrolled/ number of eligible women as found by assessing demographics of women scheduled for induction as per birth unit records
Pt demographics of those enrolled and not enrolled (age, indication for induction, gestational age)	Patient chart
Recruitment trends/ days/ time of increases recruitment	RA recruitment data
Staff Physician, resident and charge nurse at times of enrollment	Hospital records, RA will assess when in triage
Rate of protocol compliance	Assessment of appropriate inclusion/ exclusion criteria from chart, feedback from RAs
Physician/ resident/ nursing satisfaction and attitudes towards recruitment	Semi-structured interviews q3 months
Patient satisfaction/ attitudes towards recruitment	Patient surveys
Environmental, technical, patient, staff issues, data collection issues that facilitate recruitment or deter from recruitment	Semi structured interviews q3 months

The study process will be evaluated every three months. The Steering committee will review the recruitment data, interviews and patient surveys, resulting in changes in the execution of the pilot for the next 3 months, with the goal of a) improving recruitment rate through strategy development and b) discovering unforeseen challenges to the success of the study. This information will ultimately be incorporated into the large scale study protocol.

Ethics:

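### The 20% success rule does not match the plan's own accrual requirement, which is the share of eligible women approached times the share of those who consent, and the rule's denominator is inconsistent

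*Combined protocol and SAP*

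**What the plan says.** The Background section sets out the accrual case for the large trial. It names a target, "which will require the enrolment of 1442 women", and a pool: "there are 5,437 women who will meet entry criteria in the GTA-OB network each year". It joins them with a condition: "if 1/2 are approached, 20% will need to consent to complete the trial in 3 years". The pilot is to show whether that rate is achievable.

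The success rule, under Anticipated outcomes, is one threshold: "A recruitment rate of at least 20% will be considered a success". No section sets a target for the share of eligible women approached.

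The denominator of the 20% is described in different ways:

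- **Approached women.** The Primary outcome paragraph reads "The percentage of eligible women who are approached to participate in the study that are enrolled and randomized", and the opening sentence of Anticipated outcomes agrees.
- **Eligible women, with no mention of approach.** This is the wording of the main question in the abstract, of the section on capturing outcome measures (where research assistants keep the counts), and of the Analysis section.
- **Eligible women found from birth unit records of scheduled inductions.** This is the recruitment-rate row of the table under Anticipated outcomes.

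The Exclusion Criteria include "No one available to perform randomisation". The Sample Size section expects some women to be missed: "Not all inductions will take place during day time hours or during weekdays at Sunnybrook".

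**The concern.** Feasibility here is a product of two rates, and a threshold on one of them cannot settle it. A pilot could reach 20% consent among the women its research assistants happened to meet and be declared a success, although coverage was too thin for the large trial to finish on time. Under the other denominator the error runs the opposite way: a pilot that performed exactly as the Background section plans would be declared a failure.

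The staffing exclusion makes the count less certain. A woman who meets every clinical criterion but arrives when nobody can randomise her may be recorded as ineligible when she was in fact eligible and missed. The pilot exists to answer the feasibility question, so a rule that can mislead in either direction affects its headline conclusion.

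**Working it through.** **Inputs.** From the Background section: 1442 women, 5,437 eligible a year, one-half approached, 20% consent, 3 years, cesarean rates of 38% and 31%. From the Sample Size section: 10,000 deliveries a year at the two sites (4000 + 6000), one half nulliparous, 90% term, 25% induced, about 24 inductions a week, 10-15 women approached a week. From reference 13: 75% of induced women need ripening.

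**The plan's sample size.** Alpha and power are not stated. Assuming two-sided 0.05, 80% power and 1:1 allocation, the unpooled formula gives (1.960 + 0.842)² × (0.38 × 0.62 + 0.31 × 0.69) / 0.07² = 720.01. That rounds up to 721 per arm, or 1442 in total, which reproduces the plan.

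**The plan's accrual.** 5,437 × 0.5 × 0.20 × 3 = 1631, so 1442 is reached in 1442 / 543.7 = 2.65 years. The statement holds with some slack: at one-half approached, the consent strictly needed is 1442 / (5,437 × 0.5 × 3) = 17.7%.

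**What 3 years requires.** The share of all eligible women randomised must be at least 1442 / (3 × 5,437) = 1442 / 16,311 = 8.84%. The plan's one-half times 20% is 10%.

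**Reading A: denominator is approached women.** With consent at exactly 20%, the share approached must be at least 8.84% / 20% = 44.2%. Every row below meets the success rule.

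| Share approached | Women in 3 years | Years to 1442 |
|---|---|---|
| 50% | 1631 | 2.65 |
| 44.2% | 1442 | 3.00 |
| 40% | 1305 | 3.32 |
| 30% | 979 | 4.42 |
| 25% | 816 | 5.30 |

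Higher consent lowers the share needed: 8.84% / 22% = 40.2%, and 8.84% / 25% = 35.4%.

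**Reading B: denominator is all eligible women.** A 20% result implies 5,437 × 0.20 × 3 = 3262 women in 3 years, and 3262 / 1442 = 2.26 times the need. The planned one-half times 20% would show as 10% and fail.

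**Which reading the precision statement uses.** The sample of 130-195 is 20% of 650-975 (10-15 a week for 65 weeks). The stated lower limits follow from those counts of approached women: 0.20 − 1.96 × √(0.16/650) = 16.9% and 0.20 − 1.96 × √(0.16/975) = 17.5%. That favours Reading A, but the table based on birth unit records points to Reading B.

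**The pilot's forecast share approached.** The answer depends on the weekly count used as denominator:

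- Stated 24 a week: 10/24 to 15/24 = 42% to 63%.
- Stated inputs: 10,000 × 0.5 × 0.9 × 0.25 / 52 = 21.6 a week, giving 46% to 69%. The figure of 24 appears only if the 90% term factor is left out.
- Restricted to women needing ripening: 21.6 × 0.75 = 16.2 a week, giving 62% to 92%.

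**The case against.** The best defence is that the primary objective is the probability that an eligible woman agrees to be randomised, and the one-half is an openly stated condition. The share approached depends largely on staffing hours, which a large trial could change, and two sites with different scheduling may not represent the network. The pilot also collects relevant information: eligible women from birth unit records, characteristics of women not enrolled, recruitment by day and time, staff and environmental issues, and a steering committee review every 3 months.

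Much of this stands. It shows that the data are largely within reach and that consent deserves its own target. It does not give the success rule a link to coverage, since none of these items carries a threshold, and it does not resolve the denominator.

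Three stronger readings are tempting, and the documents do not support them:

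- *The staffing exclusion removes all missed women, so the share approached is near 100% by construction.* The exclusion list cannot literally be the denominator, because lack of consent is also on it. Read that way, every refuser would be ineligible and the rate would be about 100%, yet the plan expects 20%. The word approached in the primary outcome already drops missed women.
- *Poor coverage would leave no trace.* Birth unit records could reveal it.
- *The pilot already forecasts a share below 44.2%.* Only 10 divided by the rounded 24 gives 42%. The plan's own inputs give 46% or more, before restriction to women who need ripening.

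**Conclusion.** The concern holds as a mismatch between the success rule and the accrual requirement. Under neither denominator does 20% correspond to 1442 women in 3 years. Among approached women it is insufficient alone, because completion also needs 44.2% approached when consent is exactly 20%. Among all eligible women it is more than twice the 8.84% required.

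The documents do not show that the large trial would fail; they leave a necessary assumption without a test. The figures take 5,437 a year and 1442 as given, treat 5,437 as including women who would not be approached (the plan applies the one-half to it), and assume steady accrual across the network. The pilot remains useful, but its rule should be changed before its conclusion is relied on.

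**What to change.** 1. Use one definition of eligible throughout, based on the clinical criteria. Record women missed for lack of staff as *eligible, not approached*, identified from birth unit records, and no longer as excluded.
2. Report approached/eligible and randomised/approached separately, by site and time of day.
3. Keep at least 20% of approached women randomised as the consent target.
4. Judge large-trial feasibility on the product: at least 8.84% of all eligible women randomised (1442/16,311). A product is better than a fixed 44% floor on approach, because it lets higher consent offset lower coverage.
5. If only the consent target is met, conclude that 3-year completion is not shown at the pilot's level of coverage.

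The cost is protocol wording and one extra log count from records already in use. Compared with a rule on approached women alone, success becomes slightly harder to declare. The count should start with recruitment, because missed women who are not logged may be hard to recover later.

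### The recruitment rate is defined on eligible women while non-consent is an exclusion, and antenatal refusals have no counting rule, so the rate can be biased upward

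*Combined protocol and SAP*

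**What the plan says.** On timing of consent, the section on how participants are identified and followed states: "Patients may choose to sign a consent form for the study in the antenatal period, or on presentation for cervical ripening". It then describes the approach on the day: "Patients presenting for cervical ripening and meeting entry criteria will be invited to participate in the study and informed consent will be obtained". The Exclusion Criteria include "Lack of consent".

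The denominator of the primary outcome is worded in three ways:

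- **Eligible and approached.** The Primary outcome paragraph has "The percentage of eligible women who are approached to participate in the study that are enrolled and randomized". The text under Anticipated outcomes agrees.
- **Eligible, as counted by research assistants.** The section on capture of outcome measures has "number of women who undergo the randomized intervention divided by the number of women who are eligible", and adds "These numbers will be kept by the research assistants enrolling participants in the trial". The Analysis section also divides by eligible women, with no mention of approach.
- **Eligible, from hospital records.** The table under Project Outcome Evaluation Metrics has "Number of women enrolled/ number of eligible women as found by assessing demographics of women scheduled for induction as per birth unit records".

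The numerator varies too: women randomised in the first version, women who undergo the allocated intervention in the second, and women enrolled in the third. None of these places says that eligible means eligible apart from consent, and no section says how an antenatal refusal is recorded. Success is a recruitment rate of 20% or more.

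**The concern.** There are two linked problems.

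The first is a conflict of definitions. If non-consent makes a woman ineligible, and the outcome is a proportion of eligible women, then decliners fall outside the outcome that is meant to measure how many decline. This applies to refusals at any time, on presentation as well as antenatally.

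The second is an asymmetry in what is recorded. The Ethics section has research assistants obtain written consent from all patients, and they carry out the randomisation, so every acceptance that ends in randomisation passes through the people who keep the counts. A refusal given antenatally, for instance to a clinician who handed over the information package, need not reach them. When that woman later presents, she can be read as failing an entry criterion, so she may not be invited again or counted as approached.

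The recruitment rate decides whether the large trial is judged feasible. A rate that counts acceptances in full and refusals in part could cross 20% when the true rate is too low.

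**Working it through.** **1. What the plan's own arithmetic counts.** The Sample Size section gives 630 to 975 women approached, an expected rate of 20%, and 95% intervals of 16.9% to 23.3% and 17.5% to 22.7%. Exact (Clopper-Pearson) intervals give:

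| Enrolled / denominator | 95% interval |
|---|---|
| 126/630 (all approached) | 16.94% to 23.34% |
| 195/975 (all approached) | 17.53% to 22.65% |
| 26/130 (the stated sample as denominator) | 13.5% to 27.9% |
| 39/195 (the stated sample as denominator) | 14.6% to 26.3% |

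The stated intervals reproduce with all approached women as denominator, and not with 130 or 195. The intended denominator therefore includes decliners.

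**2. What the exclusion criterion gives if read literally.** With every decliner ineligible, the denominator equals the numerator and the rate is 100%. This contradicts step 1 and the 20% target. It shows that the wording needs repair; it is not an estimate of bias.

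**3. The rate the large trial needs.** From the Background: 1442 women, 5,437 eligible per year, half approached, 3 years.

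1442 / (5,437 × 1/2 × 3) = 1442 / 8155.5 = 17.7%

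**4. Effect of uncounted antenatal refusals.** Let d be the share of all eligible women offered the study who decline antenatally and go uncounted. The documents give no value for d, so these are illustrations.

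Observed rate = true rate / (1 − d)

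| True rate | d | Observed rate |
|---|---|---|
| 17.7% | 11.6% | 20% |
| 16% | 20% | 0.16/0.80 = 20% |
| 15% | 25% | 0.15/0.75 = 20% |

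The first row uses d = 1 − 0.1768/0.20 = 11.6%. A true 17.7% is enough for the large trial, so passing there does no harm. A misleading pass at an observed 20% needs d above 11.6%, which is about 14% of decliners (0.116/0.823).

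In counts: of 650 women offered the study, 104 enrol (16%). If 130 antenatal decliners (20% of 650) go unlogged, the rate becomes 104/520 = 20%.

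**5. The same effect as a share of decliners.** Let f be the share of decliners left out, and p the true rate.

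Observed rate = p / [p + (1 − p)(1 − f)]

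An observed 20% then corresponds to a true 18.4% at f = 10%, 16.7% at f = 20%, and 14.9% at f = 30%. A true 15% reaches 20% at f = 29%, which agrees with step 4 (0.25/0.85 = 29%).

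**6. Comparison with planned precision.** The half-widths of the stated intervals are (23.3 − 16.9)/2 = 3.2 points and (22.7 − 17.5)/2 = 2.6 points. The shifts of 4 and 5 points in the last two rows of step 4 exceed these, and a larger sample would not reduce them.

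**The case against.** The strongest case is that the plan plainly intends to count decliners and partly provides for it. The intervals include them. The questionnaire rule reads "All approached women, whether they consent to be part of the study or not, will be invited to complete a short questionnaire", and the metrics table asks for demographics of women not enrolled. The birth-unit list in that table does not depend on who was approached, so an antenatal decliner scheduled for induction would stay on it. Women are invited when they present, which gives a second chance to record a refusal. No antenatal refusal that ends a woman's candidacy is described.

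The direction is also open. Women offered the study antenatally who then labour spontaneously would lower the rate if they were kept in the denominator. A denominator of all eligible women, not only those approached, would lower it as well.

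Much of this stands. A reader might infer that the rate is biased upward, or that the exclusion removes every decliner in practice. The documents support neither: the first is only a risk, and the second contradicts the plan's own calculation.

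The objection does not close the gap:

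- Eligibility must still be applied to the birth-unit list, and consent is written into eligibility.
- The plan does not say whether that list or the research assistants' count governs, and two places limit the denominator to women approached.
- The invitation on presentation covers women who meet entry criteria, which a prior decliner arguably does not.
- The questionnaire is given when the research assistant makes the approach, so it need not reach a woman who refused earlier to someone else.
- Women in spontaneous labour fail the entry criteria, which largely removes the downward route. Nothing as clear guards against the upward one.

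**Conclusion.** The point holds as a defect of definition with a possible upward bias. The listing of non-consent as an exclusion conflicts with a primary outcome based on eligible women, and the denominator is not the same from section to section. Under the version limited to women approached, antenatal refusals can go uncounted while acceptances that lead to randomisation are always counted.

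The size cannot be estimated from the documents. For the illustrative values, a true rate of 15% or 16% would be reported as 20% if 25% or 20% of eligible women declined antenatally and were not logged. Both true rates are below the 17.7% that the Background figures imply. This rests on the assumed values of d and on an approach being logged only at presentation. If every antenatal refusal is logged, or if the birth-unit list is used with eligibility judged apart from consent, antenatal decliners who present for induction stay in the denominator and this bias does not arise. Because the 20% rule has no margin stated around it, the matter should be settled before the rate is analysed.

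**What to change.** - Move non-consent from the exclusion criteria to a list of reasons for non-enrolment.
- Define the denominator once and use it in the Primary outcome, outcome capture, Analysis and Project Outcome Evaluation Metrics sections: women presenting for cervical ripening who meet all criteria other than consent and were offered the study at any time, antenatally or on presentation. State one numerator to go with it.
- Log every antenatal refusal, and count the woman as approached and not enrolled if she later presents and meets those criteria.
- Leave women who never present for ripening out of both numerator and denominator, whether they had accepted or declined.
- Apply the criterion on availability of someone to randomise in the same way to women who accepted and women who declined antenatally.

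The cost is protocol wording and one field in the screening log. The reported rate may be slightly lower than under the looser definition. Nothing in clinical care changes.

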A national survey of obstetricians showed a high degree of interest in trial participation. It also found the majority of obstetricians (85%) prefer prostaglandins because of ease of use, and a perception of patient preference,² (although this is not supported in the literature).^{22,23} This survey demonstrated sufficient interest in a trial, and that the important question to ask that would result in clinical practice change is “Do Foleys filled to 80ccs result in a lower risk of cesarean than prostaglandins?”

Most obstetricians have used Foleys in the last year², demonstrating that the skills needed to make use of Foleys filled to 80cc are already in place. To facilitate the translation of Foley placement skills to our future obstetricians, we have also developed a Cervical Ripening Training Model²⁴.

Other studies have made use of Foleys filled to high volumes without evidence of adverse effects²⁵⁻²⁷, and Foleys have generally found to have a higher safety profile than prostaglandins, including decreased overall pain, decreased strong contractions causing changes in the fetal heart rate, and decreased postpartum hemorrhage^{8,20}. Our team has also done materials testing and found a standard 30cc Foley has a rupture volume of 160cc +/- 11.8cc²⁸.

A trial is needed to assess if Foleys filled to 80ccs can decrease the risk of cesarean. However, prior to this, **a pilot is required to demonstrate the feasibility of successful recruitment, and to understand unforeseen challenges and rate limiting steps that may prevent the successful completion of the trial.**

Description of the team

[name]: PI, Maternal Fetal Medicine specialist, clinician investigator at Sunnybrook Health [name] in Health Research Methodology. Assistant Professor, University of Toronto, Associate Scientist at the Sunnybrook Research Institute. She will oversee all aspects of the project (40% protected time).

[name]: Chief of Maternal-Fetal Medicine at Sunnybrook Health Sciences Centre, Director of Women and Babies Research Program at Sunnybrook Research Institute.

Chair of the GTA-OBS network, Professor in the department of obstetrics and gynecology at the University of Toronto. He has contributed to the design of the trial, and will provide leadership and support through Sunnybrook and the GTA-OB network (1/2 day/week)

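### The serious adverse event list, read as written, does not require recording a fetal death between randomisation and birth

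*Combined protocol and SAP*

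**What the plan says.** The combined protocol and SAP describes follow-up of enrolled women in the last paragraph of How will participants be identified and followed?. It gives two kinds of delivery data.

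- Delivery details: "RAs will record in Redcap the date and time of delivery for enrolled women, as well as mode of delivery (vaginal or cesarean section").
- Safety: "any serious adverse events (maternal death or ICU admission, neonatal death or unplanned ICU admission").

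The bracket in the safety item holds four events, two for the mother and two for the baby. It is not introduced by *for example*, *such as* or *including*.

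On fetal status at entry, Inclusion criteria requires "Live, singleton, cephalic fetus", and Exclusion Criteria rules out "Non-viable fetus". On timing, the follow-up section has eligible women approached when they come in for ripening; a research assistant takes consent and then obtains the allocation online. Women already in labour or contracting regularly are excluded.

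No other section defines a serious adverse event or sets out a reporting procedure. The outcome table under Project Outcome Evaluation Metrics has no safety row. Fetal death and stillbirth are not named anywhere as events to record.

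**The concern.** The list evidently means to capture death of the mother or the baby. For the baby, however, it starts at live birth. The randomised methods act before that, during ripening and the labour that follows, and this is the interval the list leaves out for the fetus.

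The background itself treats the fetus as exposed in that interval. Under Foundational work by the team, one safety difference claimed for Foleys over prostaglandins is "decreased strong contractions causing changes in the fetal heart rate".

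What is at stake is a complete count of deaths among the babies of randomised women. If the bracket is followed literally, that count could omit a death before birth. Project Outcome Evaluation Metrics says that what is learned in the pilot will feed the large-scale protocol. The same gap would pass to the planned trial of 1442 women if the list were reused, although the documents do not say that it will be.

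**Working it through.** The plan states no figure on this point, so there is none to reproduce. The check is one of wording, followed by a short calculation for context.

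**Step 1. Is the event possible in this population?** Yes. Entry requires a live fetus, and a non-viable fetus is an exclusion. Randomisation takes place when the woman presents for ripening, before labour. Every enrolled fetus is therefore at risk from randomisation to birth.

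**Step 2. Does the event meet a listed item?** Take a fetal death after randomisation and before birth.

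| Listed item | Met by a fetal death before birth? |
|---|---|
| Death of the mother | No |
| Intensive care admission of the mother | No, unless she is admitted herself, and then it is recorded as a maternal event |
| Neonatal death | No; the term applies after live birth |
| Unplanned intensive care admission of the newborn | No; a stillborn baby is not admitted |

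**Step 3. Would another recorded field reveal it?** The remaining delivery data are date, time and mode. A stillbirth has all three, and they look the same as for a live birth. No field for vital status at birth is described.

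**Step 4. Does any other section widen the list?** Data Collection, the section on capturing outcome measures, Analysis, Project Outcome Evaluation Metrics and Ethics contain no safety definition.

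**Step 5. How likely is the event in the pilot (context only)?** The documents give no fetal death rate, so the rates *p* below are assumptions. The number randomised, *n* = 130 to 195, is from Sample Size calculation. The chance of at least one event is 1 − (1 − *p*)^*n*.

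| Assumed rate | *n* = 130 | *n* = 195 |
|---|---|---|
| 0.2 per 1000 | 1 − 0.9998^130 = 2.6% | 1 − 0.9998^195 = 3.8% |
| 1 per 1000 | 1 − 0.999^130 = 12% | 1 − 0.999^195 = 18% |
| 3 per 1000 | 1 − 0.997^130 = 32% | 1 − 0.997^195 = 44% |

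The expected number of events stays below one throughout, from 130 × 0.0002 = 0.026 to 195 × 0.003 = 0.585. The event is rare but possible. The width of the range reflects the assumed rates, not anything in the plan.

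**The case against.** The strongest reply is that the operative word is *any*, and that the bracket may only illustrate. A research assistant who learns of a stillbirth might well report it. The RedCap form and any ethics-board reporting procedure are not in the supplied text, so what the form asks cannot be checked. This stands in part. That the list is exhaustive is a reading of the bracket, though the natural one. A reader might go on to infer that a stillbirth would go unrecorded in practice. The documents do not support that; they show only that the wording does not require recording it.

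A second reply is that this is a feasibility pilot. Objectives names recruitment and process evaluation. Analysis covers enrolment and process outcomes only. The sole success rule is recruitment of at least 20%. A missed event would change no planned estimate or decision. This stands in full. A reader might infer that a clean safety count is meant to support going on to 1442 women, so that one missed death would alter that step. No section contains a safety conclusion or a safety criterion for progression.

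A reader might also fault the list for leaving out the other safety differences in the background, "decreased strong contractions causing changes in the fetal heart rate, and decreased postpartum hemorrhage". That does not follow. They are reported there from earlier work, they are not pilot outcomes, and nothing in the plan classes them as serious adverse events. Leaving them off a list of deaths and intensive care admissions is no inconsistency.

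**Conclusion.** The point holds as a gap in a stated definition. Read as written, the serious adverse event list counts a death after live birth and does not require recording a death between randomisation and birth, in a trial that enrols only women with a live fetus. No other described field would show it.

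The conclusion rests on two assumptions: that the bracket defines the events and does not merely illustrate them, and that no document outside the supplied text widens the list.

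The consequence is limited to the completeness of safety recording. The event should be rare, and its frequency cannot be derived from the documents. The recruitment proportion, its precision and the 20% success rule do not change. This is a cheap improvement of low severity.

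**What to change.** In How will participants be identified and followed?, and in the matching RedCap form, add *fetal death or stillbirth after randomisation* to the listed events. Equivalently, replace the neonatal death item with *fetal or neonatal death after randomisation*.

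The cost is one extra field in data that research assistants already enter for each delivery. The sample size, the primary analysis and the conduct of treatment are untouched.
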